## **7. Analysis of secondary objectives**

7.1. To assess whether the study regimen also cures low-level rifampicin resistant TB

The interaction between treatment differences and initial rifampicin resistance mutations detected will be tested in the logistic regression model from the main analysis. Initial rifampicin resistance mutations detected is categorized as:

- None
- Low-level
- High

7.2. To assess the effectiveness of FDA vital staining screening at two weeks of treatment for early switch of non-responding rifampicin resistant TB to MDR-TB treatment, versus clinical evaluation based on fever

The proportions of initial rifampicin resistant cases started on MDR treatment within the first 2 months of primo-treatment as well as the proportion of initially present resistance never switched to the MDR regimen and not cured will be compared between the two arms using the chi-squared or Fisher's exact test.

7.3. To assess the negative predictive value of conversion at 2 weeks for relapse

The complement of the Negative Predictive value (with 95% Wilson CI) of conversion in the intervention arm will be estimated as the % of relapses among those who are already completely negative on AFB smear (auramine or FDA) at week 2.

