1.2 Rationale

Low-level resistance to rifampicin is not rare, and is easily missed by conventional DST. About 15% of all rifampicin resistance in retreatment cases is low level.^{3, 4} However, an as yet unpublished survey among our target study population suggests that this proportion may even reach 50% in new cases. Each of these mutations is rare, but a large variety exists. They are detected by absent or reduced signals with wildtype probes by molecular test formats, such as lineprobe assays and the Xpert MTB/RIF assay. This can cause substantial confusion in the interpretation and decision making when conventional DST suggests (false) rifampicin susceptibility. This is particularly problematic in the MGIT system, in which the standard 12 day read-out misses rifampicin resistance in strains with those mutations, while the control tube already meets acceptance criteria for growth. For the same reason the significance of these low-level resistance mutations remains disputed. There is nevertheless evidence that cases caused by such strains can cause outbreaks of MDR and even XDR-TB. Such strains also lead to a high frequency of adverse outcomes in individual cases, comparable to those of the high-level resistance mutations (63% failure/relapse of standard primo-treatment in our reference 2). The MIC of most low-level mutations is around the peak level in serum and tissues achieved with the standard dose of rifampicin. This could explain why more MDR with these mutations seem to be curable with the unmodified Cat. 1 or 2, but often resulting in subsequent relapse.

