4.3 Sample size

The sample size selected is 1000 patients (500 randomized to intervention, 500 to control). The study will be conducted in eight DF Bangladesh outpatient clinics with an LED TB fluorescence microscopy laboratory that register about 2000 TB cases per year of which 65% are smear-positive pulmonary TB (new or retreatment). Enrolment will target 1000 randomised smear-positive pulmonary TB patients. Given an expected 5% refusal rate, it is expected that recruitment will require 9-10 months.

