8.3.4 Secondary and tertiary analysis

Secondary Objectives

1. *To assess whether the study regimen also cures low-level rifampicin resistant TB*

Adverse treatment outcomes will be described and compared among treatment groups in subgroups defined by initial rifampicin resistance mutations (performed in all patients) detected:

- none

- low-level
- high

2. *To assess the effectiveness of standard auramine versus FDA vital staining screening at two weeks of treatment for early switch of non-responding rifampicin resistant TB to MDR-TB treatment*

The proportion of initial rifampicin resistant case detected by FDA (i.e. the sensitivity of FDA) will be estimated together with 95% CI. The same analysis will be performed for auramine or ZN AFB smears and compared with FDA. Also the number of referrals needed with both techniques will be compared.

3. *To assess the negative predictive value of conversion at 2 weeks for relapse*

The Negative Predictive value (and 95% CI) of conversion in the intervention arm will be estimated as the % of relapses among those with a minimum 1 log decline in the number of AFB, or who are already negative or only scanty positive on AFB smear (auramine or FDA) at week 2.

4. *To estimate the proportion of acquired rifampicin resistance among failures and relapses*

Proportions will be estimated together with 95% confidence intervals, using the number of failure / relapse cases without mutation detected at diagnosis as the denominator and comparing intervention and control arms.

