8.4 Sample size and power

The sample size of two times 500 patients is a trade-off between precision and exposing an excessively high number of patients to potentially more toxic treatment. Power has not been taken into account, but if the results are favourable large scale cluster-randomized study will be designed to bring definitive proof.

The registered incidence of clinically apparent hepatitis from any cause during TB treatment is 1.5% for the study population. With the proposed sample size, an increase by at least 2% compared to the control arm will attain statistical significance ($p=0.047$).

With the standard (=control) regimens and definitions, about 2% failures and 2% relapses are currently notified by the DF project, but only 50% of those are culture-positive, and about half of the culture positive failures and relapses are rifampicin-resistant. Overall cure rate (new and retreatment cases together) is close to 90%, with 4% default and 4% deaths. Based on the data from 2010 about 20 cases with rifampicin resistance may be enrolled, 10 in each arm. We estimate that the more effective study regimen plus early detection of serious drug resistance rolled over to MDR-TB

treatment will prevent drug resistant failure and relapse, reduce rifampicin susceptible relapse to an estimated two third, and reduce death and default because of unrecognized rifampicin resistance to 80% of the control arm. This total estimated reduction of unfavourable outcome from 10% to 7% remains non-significant with the targeted enrolment of two times 500 cases. With 80% power and 95% confidence level, 2 x 1421 patients would have to be enrolled, which is not feasible and also difficult to justify. However, a slightly larger reduction of unfavourable outcome from 10% to 6.5% comparing two arms of 500 cases each would already result in a significant p-value. Additional evidence will be obtained studying *rpoB* mutations, initially (all smear-positives) and at time of failure or relapse (only in the few such cases expected). Absence of low-level resistance mutations only among patients with unfavourable outcome on the high-dose arm, while they were present among new cases in both arms, will be interpreted as additional evidence of effectiveness of the increased dosing.

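### SAP 7.1 tests the low-level resistance objective only through an interaction that often has no finite estimate with the few resistant patients expected

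*SAP*

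**What the plan says.** SAP 7.1 covers the objective in one sentence plus a list of three mutation categories (none, low-level, high): "The interaction between treatment differences and initial rifampicin resistance mutations detected will be tested in the logistic regression model from the main analysis". The main model, in SAP 6, is a logistic regression with arm, hospital and new/retreatment stratum. SAP 7.1 names no test statistic, interval or small-sample method.

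Protocol 8.3.4 plans something different for the same objective: "Adverse treatment outcomes will be described and compared among treatment groups in subgroups defined by initial rifampicin resistance mutations". Protocol section 3 describes the objective in the same way.

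On numbers, Protocol 8.4 says "Based on the data from 2010 about 20 cases with rifampicin resistance may be enrolled, 10 in each arm". Protocol 1.2 gives the low-level share: "About 15% of all rifampicin resistance in retreatment cases is low level", and an unpublished survey "suggests that this proportion may even reach 50% in new cases". For outcomes with such strains it cites "63% failure/relapse of standard primo-treatment in our reference 2" and calls them comparable to those of high-level mutations.

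SAP 4.2 removes from the outcome analysis patients found rifampicin-resistant and switched to the MDR regimen before any outcome applies.

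**The concern.** A logistic interaction coefficient is finite only if every cell that defines it contains both patients with the event and patients without it. With a handful of low-level resistant patients per arm, an empty, all-event or no-event cell is likely, and maximum likelihood then diverges.

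The failure falls on the result the trial hopes for. Protocol 8.4 would read the absence of low-level mutations among adverse outcomes on the high dose as added evidence of effectiveness. That result is a zero-event cell, where the estimate does not exist.

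The question is also off target. The interaction asks whether the treatment odds ratio differs between mutation groups. The objective asks how patients with low-level resistance do on the regimen. More than a footnote depends on this, because possible favourable effects on low-resistance mutations are a stated input to the decision on the follow-on trial (Protocol 2.1 and 8, SAP 1).

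**Working it through.** **The plan's own figure.** The documents give no power or precision for this objective. The 20 resistant cases can be checked: Protocol 1.1 reports 2% MDR-TB among new cases in the 2010 survey, and 1000 × 0.02 = 20, or 10 per arm.

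**Low-level patients per arm.** 10 × 0.15 = 1.5 and 10 × 0.50 = 5, before the MDR-switch exclusion.

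**Chance of no finite estimate.** Let each of the 10 resistant patients in an arm be low-level with probability q and have an adverse outcome with probability p. The low-level cell is usable if it holds at least one patient with and one without an adverse outcome:

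U(q, p) = 1 − (1 − qp)^10 − (1 − q(1 − p))^10 + (1 − q)^10

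- U(0.50, 0.63) = 1 − 0.685^10 − 0.815^10 + 0.5^10 = 0.849
- U(0.50, 0.10) = 1 − 0.95^10 − 0.55^10 + 0.5^10 = 0.400
- U(0.15, 0.63) = 1 − 0.9055^10 − 0.9445^10 + 0.85^10 = 0.261
- U(0.15, 0.10) = 1 − 0.985^10 − 0.865^10 + 0.85^10 = 0.103

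The chance of a non-finite low-level interaction is 1 − U(control) × U(intervention). Control risk is 63% (Protocol 1.2). The intervention risk of 10% is an assumption.

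| Low-level share | No effect (63% vs 63%) | Benefit (63% vs 10%) | Zero events on intervention |
|---|---|---|---|
| 50% | 1 − 0.849² = 28% | 1 − 0.849 × 0.400 = 66% | 100% |
| 15% | 1 − 0.261² = 93% | 1 − 0.261 × 0.103 = 97% | 100% |

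If half the resistant patients left after an MDR switch (an assumption; the documents give no share), q halves and the range becomes 75% to over 99%. In the most favourable corner (50% share, no exclusions, no effect) the answer depends on how cell sizes vary: 20% with exactly 5 per arm, 28% as above, 35% with Poisson sizes.

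**What the test returns.** Illustration: low-level adverse outcomes in 0/5 intervention and 3/5 control patients; no-mutation group 34/490 vs 49/490; high group 3/5 vs 3/5; hospital and stratum left out.

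- Wald, low-level term: p = 0.999 or above (the exact value depends on where the software stops iterating)
- Likelihood ratio: p = 0.038 on 1 df (low-level term), 0.11 on 2 df (the whole three-level interaction)
- Fisher within the low-level group: p = 0.17

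With eight sites and stratum added (assumed 10% retreatment, sites at random), Wald gives 1.00, likelihood ratio 0.028 and 0.088, and Firth-penalised likelihood ratio 0.082. The pattern is the same.

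Wilson 95% intervals stay finite: 0–43% for 0/5 and 23–88% for 3/5.

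**What a small-sample method can do.** With n patients per arm, all adverse in one and none in the other, Fisher's two-sided p is 2/C(2n, n): 0.33 for n = 2, 0.10 for n = 3, 0.029 for n = 4, 0.008 for n = 5. For 63% vs 10%, Fisher's power is about 0.3% at a 15% share and 23% at 50%.

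**The case against.** Several points on the other side are sound.

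- **Test not named.** A reader might infer that the SAP prescribes a Wald test and so returns p near 1. It does not; SAP 7.1 only says the interaction will be tested. Wald is the usual software default and is what Rubin's-rules pooling (SAP 6.2b) leads to if applied here, but a likelihood-ratio test would give a usable p-value. It would still give no finite effect estimate.
- **The 15% share is for retreatment cases.** Retreatment patients have rapid susceptibility testing before treatment, and those found resistant are not enrolled (Protocol 4.2 and 5.3). Enrolled resistant patients should be mainly new cases, so the higher share is more relevant. It is an upper figure, though, and the MDR-switch exclusion pulls the other way.
- **Cure of every case is not the trigger.** Death, default and most loss to follow-up also count as adverse (SAP 4.1.1 and 4.2), so bacteriological cure of every low-level case need not give a zero cell.
- **The protocol analysis was not withdrawn.** Protocol 8.3.4 still stands, and Protocol 8.1 puts estimation ahead of testing. But SAP 7.1 omits that analysis, and it is the document the statistician will follow.
- **No estimator creates information.** The main limit is the number of patients.

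The SAP's existing safeguards do not reach this analysis. The low-events fallback in SAP 6 only simplifies covariates, which does not cure an empty or zero cell. The sufficient-events condition in SAP 6.1 and the Fisher option in SAP 7.2, 7.5 and 7.6 are not carried into 7.1.

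**Conclusion.** The point holds as a choice of analysis unsuited to the expected data. On the documents' figures the low-level interaction often has no finite estimate: about 28% to 93% of trials with no effect, 66% to 97% under the assumed benefit, and always with no adverse outcomes in the low-level intervention cell. The interaction also does not answer the stated objective, and SAP 7.1 leaves out the within-group description that the protocol planned.

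The documents do not support saying that the estimate will usually fail in every scenario, since the 50% share with no effect and no exclusions is a counter-example. Nor do they support saying that no usable p-value can be obtained.

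The size rests on 10 resistant patients per arm, a low-level share of 15% to 50%, a control risk of 63% in these patients, an assumed 10% on intervention, and an unknown share excluded after an MDR switch. This is a secondary objective in an estimation pilot, so the change is worth making but does not touch the primary analysis.

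**What to change.** In SAP 7.1:

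1. Make the main analysis the count and proportion with an adverse outcome, per arm, within the none, low-level and high groups, with Wilson or exact 95% intervals.
2. Support it with Fisher's exact test or Firth-penalised logistic regression within the low-level group. If an interaction is kept, fit it by Firth penalised likelihood.
3. Report by arm and mutation group how many resistant patients were excluded after an MDR switch. The two-week screen that triggers switching differs by arm (FDA smear versus fever), so the resistant patients who remain may be selected differently. An exact test does not remove that.
4. State that this gives finite, interpretable estimates but little power: Fisher cannot reach p < 0.05 with 3 or fewer patients per arm.

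The cost is a change of SAP wording. No new data are needed, since the pre-treatment *rpoB* sequencing and the treatment switches are already recorded.

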2. Prevention of development of MDR- TB and cure of low-level rifampicin-resistant TB (MDR or monoresistant) with this more bactericidal Cat. 1.
3. Very early start of the MDR regimen for high-level rifampicin-resistant disease (MDR or monoresistant), reducing the risk of death and default and preventing accumulation of further or higher-level drug resistance to H, Z or E. This approach better preserves the efficacy of the latter drugs which are all used in the MDR regimen.
4. Reduction of toxicity from injectable drugs and ethambutol during the MDR regimen, by abolishing the Cat. 2 regimen (no streptomycin used prior to kanamycin in the MDR regimen, thus avoiding cumulative vestibular-, renal- and ototoxicity; also ethambutol ocular toxicity is cumulative across courses of treatment). Amplification of first-line drug resistance (S, H, Z and E) will be further avoided by dropping Cat. 2. As streptomycin resistance disappears in the population, streptomycin might eventually remain available as a key drug for MDR (re)treatment, alternative to second-line injectables.
5. Concordance between geno- and phenotypic rifampicin DST would improve if the low-resistance mutations have no impact on high-dose rifampicin treatment. Moreover, new molecular DST formats omitting these now irrelevant mutations could then be simplified and made fully specific for rifampicin resistance. Such tests would identify only mutations highly predictive of bacteriologically poor outcome even with the high-dose regimen. This would at the same time avoid errors of current molecular tests with resistance detection based on the absence of, or poor binding to, wildtype DNA probes: silent mutations, poor reactions and reading errors would no longer interfere with genotypic resistance testing.

Other groups are also studying high-dose rifampicin, yet their aim is to shorten Cat. 1 treatment without increasing relapse. These clinical trials would thus provide complementary information and might show further gains that are possible with increased dosing, e.g. in paucibacillary disease.

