## 1. Introduction

This Statistical Analysis Plan (SAP) provides a detailed and comprehensive description of the main, pre-planned analyses for the study "Optimization of the TB treatment regimen cascade", including the recently approved interim analysis. The purpose of this study is to compare a high-dose rifampicin standard TB regimen of 6 months duration with the standard TB regimen in respect to adverse treatment outcome (relapse, failure, death and default) and toxicity, in smear-positive pulmonary TB cases. The study conduct is described in the Protocol.

These planned analyses will be performed by the statistician(s) at the Clinical Trials Unit of the Institute of Tropical Medicine (Antwerp) in collaboration with the research consortium. The analysis results will be described in a statistical analysis report, to be used as the basis of the primary research publications. This document describes statistical methods for the primary and secondary objectives of the study as defined by protocol. Additional analyses may be performed but are not covered by the current analysis plan.

Analyses will be performed at three time-points.

1) Assessment of referral for rapid DST plus its outcome based on the auramine and/or FDA decline for the patients randomized in the intervention arm versus persisting fever, for the patients randomized in the control arm, 2 weeks after the first 500 enrolled patients (intervention + controls) reached two weeks follow-up. With this analysis we want to assess whether any of those can really be used as an early indicator of serious rifampicin resistance, and also assess the impact of improvement of staining techniques that were made after the first ITM monitoring visits. The results in terms of resistance missed / correctly suspected will be analysed based on the initial genetic rifampicin resistance data which will by that time also be available for part of these patients.

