#### *In the control group*

The number (%) of referrals to rapid DST (based on body temperature) will be presented. Counts (%) of the rapid DST result will be presented.

The percentage of resistance missed will be compared between groups using the Chi-square or Fisher's exact test.

All analyses will be stratified on new vs retreatment cases. Analysis in the intervention group will be additionally stratified on period (2014 vs 2015).

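### The early-switch proportion in SAP 7.2 pools low-level with high-level rifampicin resistance, which biases that measure against the intervention arm

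*SAP*

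**What the plan says.** Objective 2 concerns "early switch of non-responding rifampicin resistant TB to MDR-TB treatment, versus clinical evaluation based on fever". SAP 7.2 gives it two measures, each compared between arms by a chi-squared or Fisher's exact test. The first is "The proportions of initial rifampicin resistant cases started on MDR treatment within the first 2 months of primo-treatment". The second is the "proportion of initially present resistance never switched to the MDR regimen and not cured". Protocol section 3, objective 2, has the same pair. Neither document splits the first measure by mutation level, although SAP 7.1 already sorts initial mutations into none, low-level and high.

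Protocol 1.1 lists two separate benefits. One is "cure of low-level rifampicin-resistant TB (MDR or monoresistant) with this more bactericidal Cat. 1"; the next is a very early MDR start for high-level disease. Protocol 1.2 gives the mix: "About 15% of all rifampicin resistance in retreatment cases is low level", and an unpublished survey in the target population "suggests that this proportion may even reach 50% in new cases".

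The first interim analysis asks whether the two-week signs can serve as an "early indicator of serious rifampicin resistance" (SAP 1). SAP 5 then states: "The percentage of resistance missed will be compared between groups". It does not say which resistance forms the denominator.

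**The concern.** Under the week-2 rule (SAP 2.1, intervention testing), a patient whose FDA count has fallen by at least 1 log, or who is already negative, stays on the regimen and is not referred. A low-level carrier who responds in this way and is cured is a success for objective 1. In the first measure of SAP 7.2 the same patient adds to the denominator and not to the numerator.

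The measure also means different things in the two arms. Controls receive the standard dose, on which protocol 1.2 reports 63% failure or relapse for low-level strains. An unswitched low-level control is therefore more often a real miss than an unswitched low-level intervention patient would be if the double dose works as hoped. The better it works on low-level disease, the worse FDA screening looks on this measure.

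The trial is meant to inform the resistance-screening algorithm of the larger study (protocol 2.1). A switch rate that mixes the two kinds of patient could mislead that choice.

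**Working it through.** **Inputs**
- Expected resistant patients: about 20, or 10 per arm (protocol 8.4). The 2% MDR figure for new cases in the 2010 survey (protocol 1.1) reproduces this: 0.02 × 1000 = 20, and 0.02 × 500 = 10. It is an MDR figure in new cases, used here as a proxy for all rifampicin resistance.
- Low-level share of resistance: 0.15 in retreatment cases, up to 0.50 in new cases (protocol 1.2).
- Any rifampicin-resistant result leads to MDR treatment, whatever the mutation (protocol 5.4, DST).

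**First measure.** Let *L* be the low-level share among enrolled resistant patients and *s* the fraction of low-level patients switched by 2 months. Suppose every high-level patient is switched. Then

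proportion = (1 − *L*) + *L* × *s*.

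- *s* = 0: 1 − 0.15 = 85% (all retreatment); 1 − 0.50 = 50% (all new).
- *s* = 0.5: 0.85 + 0.075 = 92.5%; 0.50 + 0.25 = 75%.
- *s* = 1: 100% in both cases.

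For a mix with share *w* of new cases, *L* = 0.50*w* + 0.15(1 − *w*). At *s* = 0, *w* = 0.25, 0.50 and 0.75 give about 76%, 68% and 59%. The documents do not give *w*. Retreatment cases found resistant before treatment are not eligible (protocol 5.3, screening visit), so the enrolled mix probably leans towards new cases.

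**Second measure.** With every high-level patient switched and cure fraction *c* among unswitched low-level patients,

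proportion = *L* × (1 − *s*) × (1 − *c*).

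- *s* = 0 and *c* = 1: 0%, the best possible value. Cure without a switch is credited.
- *s* = 0 and *c* = 0.37 (the complement of 63% failure or relapse): 0.15 × 0.63 = 9.5%; 0.50 × 0.63 = 31.5%.

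**Stratum sizes.** High-level carriers per arm: 10 × 0.50 = 5 to 10 × 0.85 = 8.5. Low-level carriers: 1.5 to 5.

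**What pooling could hide.** The documents give no switch rates, so the control rate here is assumed to be 20%, both overall and among high-level carriers. With Fisher's exact test at two-sided 5%:
- pooled, 10 per arm: power is 13% at a true intervention rate of 50%, 74% at 85% and 99% at 100%;
- high-level only, intervention rate 100%: power is 74% with 5 per arm and 94% with 8 per arm.

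As an example, 5/10 against 2/10 gives p = 0.35. In these scenarios the smaller high-level stratum loses nothing against the pooled figure, because the contrast in it is undiluted.

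**The case against.** The best reply is that SAP 7.2 does not rest on one measure. The second, in the same sentence, leaves a cured, unswitched patient out of the failures. That stands. A reader might infer that SAP 7.2 scores every unswitched resistant patient as a miss, but this is true of the first measure only. The second does not repair the first, which will still be tabulated and tested.

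A reader might also infer that even a perfect strategy could score no more than 50-85%. The documents do not support a cap. Any resistant result triggers a switch, so low-level patients who are referred and test resistant count as switched, and 100% is attainable. Protocol 1.2 also says that smear quantification is not very reproducible, so some low-level responders may be referred anyway.

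Nor do the documents support a figure of 15-50% for interim missed resistance. SAP 5 defines no denominator, and the stated aim of serious resistance points away from counting low-level carriers. That interim analysis does not affect trial conduct, and sequencing will be available for only part of its patients.

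It would also go too far to call every unswitched low-level control a true miss: 63% is not 100%, and protocol 1.2 says that some such cases seem curable on standard regimens.

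Finally, making high-level carriers the only main denominator would presume the answer to objective 1, and high-level genotype is not identical to non-response. This stands too, and it is why the pooled figure should stay.

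**Conclusion.** The concern holds for the first measure of SAP 7.2 and its counterpart in protocol section 3. Pooling the two kinds of resistance sets that measure against the aim of curing low-level disease without a switch, and biases it against the intervention as a test of early-switch screening.

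The 85% to 50% range is a scenario. It assumes that all high-level and no low-level cases are switched by 2 months; its ends are the pure retreatment and pure new-case mixes; and 50% is an upper estimate. The direction of the bias depends on the double dose acting on low-level disease, which the trial has yet to show. For SAP 5 the fault is an undefined denominator, not a demonstrated bias.

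This is a secondary objective in an estimation pilot with about 10 resistant patients per arm. It does not touch the primary analysis, but as written the first measure cannot answer objective 2 cleanly.

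**What to change.** In SAP 7.2, report the proportion started on MDR treatment within 2 months separately for the low-level and high classes of SAP 7.1, in each arm. Name the high-level row in advance as the test of early-switch screening. List low-level carriers with switch status and, at the final analysis, whether cured. Keep the all-resistant proportion and the second measure. Record the change against protocol section 3, objective 2, so that the two documents agree.

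In SAP 5, state the denominator for missed resistance and report it by the same classes, among patients whose sequencing result is available.

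The cost is a few lines of text. *rpoB* sequencing of the pre-treatment sample is already planned for every enrolled patient (protocol 5.4). The downside is small strata, about 5 to 8.5 high-level and 1.5 to 5 low-level carriers per arm, so the rows should be read as counts with intervals. Fixing the split before results are seen makes it more credible than adding it afterwards.
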